1 INTRODUCTION

CooperVision is evaluating the subjective acceptance of BiofinityToric (CooperVision) in comparison with Ultra for Astigmatism (Bausch & Lomb), when each lens is worn on a daily wear basis over one (1) month in a randomized bilateral, cross-over, dispensing study.

2 OBJECTIVES

The objective of the study is to evaluate the subjective acceptance of Biofinity Toric test lens when worn on a daily wear modality over 1 month.

The primary study measures are:

- Comfort subjective ratings (0-10 scale) and lens preference with respect to comfort (5step Likert)
- Dryness subjective ratings (0-10 scale) and lens preference with respect to dryness (5step Likert)

The secondary study measures are:

Handling subjective ratings (0-10 scale)

3 HYPOTHESIS

The study hypothesis is that Biofinity Toric (BT) 'test lens' will have equal or better subjective acceptance by wearers than the 'control lens', Ultra for Astigmatism (UT).

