11 STATISTICAL ANALYSIS AND DATA MANAGEMENT

11.1 SAMPLE SIZE CALCULATION

Sample size was calculated using the mean comfort rating data from the previous pilot PIANO study (EX-MKTG-83). The data from the PIANO-2 will be pooled with data from the pilot PIANO study, therefore anyone who participated in the pilot study will be excluded from participating in the PIANO-2 study.

A total sample size of 44 is recommended to provide a minimum power of 90 with an alpha of 0.05 in a two-tailed t-test to detect a difference of 1 comfort unit (scale of 0-10). Based on the results from the pilot study (i.e. PIANO Study) the sample size needed for PIANO-2 will be aimed at 26 to complete (i.e. total of 44 minus the 18 completed participants from the pilot study). Therefore, it is recommended that at least 30 subjects are dispensed in the PIANO-2 study, with a target of 26 to complete.

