11.2 STATISTICAL ANALYSIS

All data will be analyzed by CORE at the University of Waterloo. Data analysis will be conducted using Statistica, SPSS or SAS. Descriptive statistics will be provided on information regarding baseline variables (age, gender, refractive error distribution, etc.). Analysis of variables will be conducted separately on each eye, and data will not be pooled. For assessments conducted for each eye separately, the right eye will be used for analysis if there is no difference between eyes. If a general difference is found (e.g. for paired t-test / Wilcoxon matched pairs) between OD and OS, a comment will be provided.

A Binomial test will be used to analyze the results for the count data of subjective preferences. The number of "no preference" will be evenly distributed to the two options on the basis they would be equally likely to choose either.

Table 4 lists the primary study measures and anticipated statistical procedures.

Table 4: Study measures and anticipated statistical procedures

Variable	Analysis	Statistical test	
Analogue scales/Numeric scales/Preference scales/VA Lens parameters Biomicroscopy (continuous variables)	Effect of lens type	RMANOVA/MANOVA/ Friedman Wilcoxon matched pairs test Tukey HSD post hocs Paired t-test Chi-square test	
Biomicroscopy (ordinal variables)	Effect of lens type	Friedman Wilcoxon matched pairs test	
Analogue scales/Numeric scales/Lens parameters, Biomicroscopy (continuous)	Relationship between slit lamp findings and analogue scales	Pearson correlation - r	
Biomicroscopy (ordinal variables)	Relationship between slit lamp findings and analogue scales	Spearman correlation - rho	

The critical alpha level for statistical significance will be set at $p \le 0.05$, with no adjustments for multiple comparisons.

All participants who were evaluated will be used in the analysis. In the event of missing data, individual data points will be excluded in the analysis and not extrapolated from the collected data.

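### The hypothesis is 'equal or better', but the analysis only tests for a difference, so 'equal' has no prespecified route to support

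*Combined protocol and SAP*

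**What the plan says.** - **Hypothesis (section 3).** BT "will have equal or better subjective acceptance by wearers than the 'control lens", UT. This is the only hypothesis stated.
- **Primary measures (section 2).** Comfort ratings with comfort preference, and "Dryness subjective ratings (0-10 scale) and lens preference with respect to dryness".
- **Sizing (section 11.1).** The basis is a "two-tailed t-test to detect a difference of 1 comfort unit (scale of 0-10"), with alpha 0.05, power 90 and a total of 44. On its source: "Sample size was calculated using the mean comfort rating data from the previous pilot PIANO study". The 44 are 26 new completers plus 18 pilot completers, because "The data from the PIANO-2 will be pooled with data from the pilot PIANO study".
- **Analysis (section 11.2).** "Table 4 lists the primary study measures and anticipated statistical procedures". For the effect of lens type the table offers ANOVA-type tests, Friedman, Wilcoxon, Tukey, paired t and chi-square. Its correlations relate slit-lamp findings to scales and do not compare lenses. For preference, "A Binomial test will be used to analyze the results for the count data of subjective preferences".
- **Decision rule (section 11.2).** "The critical alpha level for statistical significance will be set at" p ≤ 0.05. No other rule is given.

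**The concern.** A test for a difference can reject equality, but it cannot establish it. The planned analysis has three outcomes: significant favouring BT, significant favouring UT, and non-significant. The first supports 'better' and the second contradicts the hypothesis. The third is what equal lenses would nearly always produce, and the plan does not say what it means. It could reflect equal lenses, or a BT deficit that the study failed to detect.

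The hypothesis counts equality as success, so its most likely outcome under equality would be interpreted after the data are seen. A margin chosen late would be especially open to challenge here, because 18 of the pooled 44 are pilot participants whose comfort data already informed the sizing.

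**Working it through.** **Inputs.** From section 11.1: N = 44 (26 + 18), two-tailed alpha 0.05, 90% power, 1 comfort unit. From section 4.1.1: a cross-over, so each participant rates both lenses. Not stated: any SD, or whether the sizing was paired. The SDs below are therefore assumptions.

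**1. Reproducing N = 44.** For a paired t-test, power = P(T > t_crit), where T is noncentral t with n − 1 df and noncentrality δ√n/σ_d. With n = 44, t_crit = 2.017. Setting δ = 1 and power 0.90 gives σ_d = 2.0 (noncentrality 1 × √44 / 2.0 = 3.32). A two-sample calculation with 22 per group gives 44 at a per-rating SD of 1.0. Converting by σ_d = σ√(2(1 − ρ)):
- ρ = 0: σ_d = √2 = 1.41
- ρ = 0.5: σ_d = 1.0

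So 44 is plausible, but it cannot be strictly reproduced without the SD. I use σ_d = 1.0, 1.41, 2.0 and 2.5. The last lies above the SD that gives the stated power.

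**2. Lenses truly equal.** P(non-significant) = 0.95 and P(significant favouring BT) = 0.025, whatever the SD.

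**3. BT truly worse.** P(non-significant), N = 44, paired t:

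| SD of differences | 0.5 worse | 0.75 worse | 1.0 worse |
|---|---|---|---|
| 1.0 | 10% | 0.2% | about 0% |
| 1.41 | 37% | 7% | 0.4% |
| 2.0 | 63% | 32% | 10% |
| 2.5 | 75% | 51% | 26% |

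**4. Can a non-significant result hide a deficit above the protocol's own 1 unit?** The 95% CI half-width is h = 2.017 × s / √44, where s is the observed SD of differences. A result is non-significant when the observed deficit is below h. Its CI includes a deficit above 1 unit when the observed deficit exceeds 1 − h. Both can hold only if h > 0.5, that is, s > 0.5 × 6.633 / 2.017 = 1.64. At s = 2.0, h = 0.61, so the window is an observed deficit of 0.39 to 0.61.

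By simulation at true SD 2.0, such results are 8% of non-significant results if the lenses are equal (0.08 × 0.95, about 8% of all trials) and 43% if BT is 0.5 worse (0.43 × 0.63, about 27% of all trials).

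**5. What a margin would deliver at this N.** The chance that the lower 95% limit clears −M when the lenses are equal is P(T > t_crit) with noncentrality M√n/σ_d. At SD 2.0:
- N = 44: 90% for M = 1, 68% for M = 0.75, 37% for M = 0.5
- 26 new completers alone: 69% for M = 1

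**6. Why a lower-limit rule is not enough.** With M = 1 and BT truly 0.5 worse, the CI lies wholly between −1 and 0 in 80% of trials at SD 1.0, 27% at SD 1.41 and 0.3% at SD 2.0 (simulation). A rule using only the lower limit would call these 'equal or better' although BT is significantly worse.

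**The case against.** **The hypothesis may be informal.** Section 2 aims only to evaluate acceptance, and section 3 can be read as an expectation in a minimal-risk study of marketed lenses. That is a fair reading, and rewording section 3 would meet it. But it is the only hypothesis given, and the sizing attached to the study is formal.

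**The gap may be small in practice.** This stands in part. Each person rates both lenses, so positive within-person correlation is plausible. At SD 1.0 a 0.5-unit deficit is missed only 10% of the time. When the observed SD is below about 1.64, every non-significant result excludes a 1-unit deficit, and what is missing is only the written rule.

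**The 1 unit could be an implicit margin.** Section 11.1 describes it only as a difference to detect. If a margin is meant, it has to be stated and justified as one.

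**Stronger readings that the documents do not support.** A reader might infer that the sponsor intends to report non-significance as equality; no section says so. A reader might also infer that 44 is the wrong number; it is consistent with the stated power at SD 2.0, and would give 90% power for non-inferiority at that SD if a 1-unit margin were justified. Nor is the whole hypothesis untestable, since the planned tests can support 'better'.

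**Conclusion.** The point holds as a mismatch between hypothesis and analysis. The 'better' half can be supported as planned; the 'equal' half cannot, because nothing in sections 3 or 11 turns a non-significant result into evidence for it. It should be fixed, but it does not make the data unusable.

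The mismatch itself rests on the text and needs no assumption. Its practical size depends on an SD that the plan does not state: a true 0.5-unit BT deficit goes undetected from 10% of the time (SD 1.0) to 75% (SD 2.5), with 63% at the SD that a paired reading of the sizing implies. These figures also assume normally distributed paired differences and pooling with the pilot to 44.

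**What to change.** Choose one option before database lock and unmasking. Both keep N and the data as they are.

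**Option A: add a margin.** In section 11.2, prespecify and justify a non-inferiority margin for overall comfort and overall dryness at the 1-month visits, without using the pilot's observed lens difference. Use the two-sided 95% CI for the paired mean difference BT minus UT, oriented so that positive favours BT. For each rating:
- 'Equal or better' only if the lower limit is above minus the margin **and** the CI does not lie wholly below zero.
- 'Better' if the lower limit is above zero.
- 'Worse, within the margin' if the CI lies wholly between minus the margin and zero.

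Report preference with its 95% CI as supportive only. Even a 22/22 split of 44 has an exact 95% CI of 35% to 65%.

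*Cost.* The sponsor is committed to a margin, and section 11.1 must state the resulting power, with and without pooling (step 5 of the working). If the justified margin is well below 1 unit, power at this N may be poor, and the sponsor should know that before choosing this option. If the true SD is small, 'worse, within the margin' becomes a likely result when BT is modestly worse (step 6).

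**Option B: restate the hypothesis.** Reword section 3 as a two-sided difference hypothesis matching the existing analysis, make no equality claim, and state that a non-significant difference will not be reported as equality.

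*Cost.* It gives up the 'equal' claim; no margin is needed.

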4 MATERIALS AND METHODS

4.1 STUDY DESIGN

4.1.1 OVERALL DESIGN

This study is a prospective, double-masked (investigator and participant), bilateral, randomized, cross-over dispensing study comparing subject acceptance of BT test lens against UT control lens.

Both test and control lenses will be used in their approved daily lens wear modality for approximately one (1) month. It is anticipated that this study will involve up to 5 scheduled visits:

Visit 1: Includes screening, baseline assessments, fitting of both lens types.

Visit 2: Dispense lens pair #1 (either test or control lens).

Visit 3: 1-month follow-up visit of lens pair #1

Visit 4: Dispense of lens pair #2 (either test or control lens)

Visit 5: 1-month follow-up visit of lens pair #2 and study exit.

The study design in shown in Figure 1.

[figure not shown]

Figure 1: Study Design

4.1.2 RANDOMIZATION

A randomization schedule will be generated using SAS or a web-based program: (www.randomization.com). An example of the format generated is given in Appendix 23. The final study randomization schedule will be generated by the CORE Data Management Team, and provided to the research assistants for use during the study. Study investigators will remain masked to the randomization schedule until the study is completed and the database is locked.

4.1.3 MASKING

Participants will be masked to lens assignment. Lenses will be dispensed to participants in a manner to maintain subject masking as described in Section 4.7.4. Investigators will be masked as much as possible.

4.2 STATEMENT OF COMPLIANCE

This protocol document has been developed in accordance with the following:

- ISO 14155 Clinical Investigation of Medical Devices for Human Subjects, Parts 1 & 2
- ICH Harmonized Tripartite Guideline for Good Clinical Practice
- The University of Waterloo's Guidelines for Research with Human Participants
- Tri-Council Policy Statement: Ethical Conduct for Research Involving Humans, 2nd
 Edition. http://www.pre.ethics.gc.ca/eng/policy-politique/initiatives/tcps2-eptc2/Default/
- Declaration of Helsinki

4.3 ETHICS REVIEW

This study will be conducted in accordance with Institutional Review Board regulations (U.S. 21CFR Part 56.103) or applicable IEC regulations. Copies of all IRB/IEC correspondence with the investigator/sponsor will be kept on file.

This protocol will be submitted to and reviewed through the Office of Research Ethics (ORE) at the University of Waterloo, Canada. Notification of ethics clearance of the application is required prior to the commencement of the study. The conduct of this study will be given clearance by the Clinical Research Ethics Committee at the University of Waterloo, Canada.

4.4 CLINICAL TRIAL REGISTRATION

This study will be registered in the clinical trials registry (https://clinicaltrials.gov/) by the study sponsor.

4.5 INFORMED CONSENT

Informed consent shall be obtained in writing from all participants prior to their enrolment in the study (Appendix 1), and before any procedure specific to the clinical investigation is carried out.

4.6 STUDY POPULATION

4.6.1 NUMBER OF PARTICIPANTS

Up to 30 participants will be dispensed / randomized with study products, with a target of 26 completing the study. Participants will be recruited using CORE records and advertising approved by the UW Office of Research Ethics (Appendices 2, 3a, and 3b). Each participant will be given a unique study specific ID number. Additionally, all participants must meet all the study inclusion and none of the exclusion criteria listed below.

4.6.2 INCLUSION AND EXCLUSION CRITERIA

A person is eligible for inclusion in the study if he/she:

- 1. Is at least 17 years of age and has full legal capacity to volunteer;
- 2. Has had a self-reported oculo-visual examination in the last two years.
- 3. Has read and signed an information consent letter;
- 4. Is willing and able to follow instructions and maintain the appointment schedule;
- Is an adapted soft contact lens wearer, who currently wears contact lenses for a minimum 3 days/week and 8 hours/day AND who anticipates no difficulty wearing CLs for 6 days/week, 10 hours /day.
- 6. Is willing to wear contact lens in both eyes for the duration of the study;
- 7. Has a minimum astigmatism of 0.75, determined by refraction;
- 8. Can be fit with the two study contact lens types in the powers available;
- 9. Has a distance visual acuity of 0.20 logMAR (approx 20/30) or better, determined by refraction:
- 10. Can achieve a distance visual acuity of 0.20 logMAR (approx 20/30) or better in each eye with the study contact lenses.
- 11. Has clear corneas and no active* ocular disease;

A person will be excluded from the study if he/she:

- 1. Is participating in any concurrent clinical trial;
- 2. Has any known active* ocular disease and/or infection;
- 3. Has a systemic condition that in the opinion of the investigator may affect a study measure;
- 4. Is using any systemic or topical medications that in the opinion of the investigator may affect a study measure;
- 5. Has known sensitivity to fluorescein dye or products to be used in the study;
- 6. Appears to have any active* ocular pathology, ocular anomaly or severe insufficiency of lacrimal secretion (severe dry eye) that would affect the wearing of contact lenses;
- 7. Is pregnant, lactating or planning a pregnancy at the time of enrolment (by verbal confirmation at the screening visit);

- 8. Is aphakic;
- 9. Has undergone refractive error surgery.
- 10. Has participated in the PIANO (i.e. EX-MKTG-83) Study.

4.6.3 REPEATED SCREENINGS

In some circumstances a repeated screening may need to be scheduled. Examples include, but are not limited to:

- 1. Incomplete information available at time of screening to determine eligibility (e.g. current lens brands worn, history from current eye care practitioner etc.)
- 2. Study procedures unable to be completed in time scheduled for visit;
- 3. Study products not available at the time of the screening visit;
- 4. A transient health condition which may affect the eye(s) (e.g. a common cold, active allergies, fatigue etc.)
- 5. The short term use of medications (e.g. antibiotics, antihistamines etc.)
- Reassessment of baseline ocular conditions (e.g. corneal and/or conjunctival staining, scars etc.)

The maximum total number of screenings permitted will be 3 i.e. 2 repeated screenings are allowed.

4.7 STUDY MATERIALS

4.7.1 LENSES

Details of study lenses are show in Table 1.

Table 1: Lens parameters to be used in this study

	Biofinity Toric	Ultra for Astigmatism
Manufacturer	Cooper√ision Inc.	Bausch & Lomb
Material	comfilcon A	samfilcon A

^{*} For the purposes of this study, active ocular disease is defined as infection or inflammation which requires therapeutic treatment. Mild (i.e. not considered clinically relevant) lid abnormalities (blepharitis, meibomian gland dysfunction, papillae), corneal and conjunctival staining and dry eye are not considered active ocular disease. Neovascularization and corneal scars are the result of previous hypoxia, infection or inflammation and are therefore not active.

	Biofinity Toric	Ultra for Astigmatism
Health Canada license #	70149	94501
EWC (%)	48%	46%
Dk/t (-3.00D)	116.0	114.0
BOZR (mm)	8.7	8.6
Diameter (mm)	14.5	14.5
Sphere power (D)	+6.00 to -6.00D (0.25 steps) +6.00 to +8.00 and -6.00 to -10.00 (0.50 steps)	+6.00 to -6.00D (0.25 steps) +6.00 to +8.00 and -6.00 to -10.00 (0.50 steps)
Cylindrical Power (D)	-0.75 to -2.25 (0.50 steps)	-0.75 to -2.25 (0.50 steps)
Axis (degree)	10° to 180° (10° steps)	10° to 180° (10° steps)

4.7.2 CONTACT LENS CARE SYSTEM

Alcon Optifree PureMoist solution (rub and rinse) will be used as the contact lens care system in this study.

4.7.3 REWETTING DROPS

Participants will not be encouraged to use rewetting drops; however, those who habitually use rewetting drops will be allowed to continue using their normal drops. Rewetting drop use will be recorded at each visit. In the event of an adverse event, rewetting drops may be given to participants.

4.7.4 CONTACT LENS DISPENSING

The lenses will be provided to the participant after being transferred, complete with blister pack solution, to a contact lens cup; this will maintain participant masking and aid investigator masking. The use of saline for rinsing the contact lens prior to insertion is permitted if necessary. Saline will not be dispensed during the study.

4.7.5 ORDERING CONSUMABLES

A stock of both study lenses will be provided by the Sponsor.

CORE will source the care solution.

CORE must maintain an accurate accounting of the study product during the study. A detailed inventory must be completed for all study supplies.

4.7.6 DISPOSING OF CONSUMABLES

This study provides consumables (lenses and lens care solution) to participants for use during the study. Worn lenses will be collected from the participants at each 1-month visit (or on discontinuation/exit from the study) and at the end of the study they will be disposed of according to UW guidelines, unless otherwise directed by the study Sponsor. Worn lenses specifically associated with adverse events/product observations may be retained either at CORE or returned to CooperVision. Typical analysis in these cases relates to inspection for damage and/ or bacterial contamination.

4.7.7 PRODUCT ACCOUNTABILITY

Accountability logs will be kept to include the number of lenses received, dispensed, unused, and returned to vendor (where relevant). All products dispensed to participants will be recorded in the participant's accountability log.

4.8 SCHEDULED AND UNSCHEDULED VISITS

This study has a total of 5 scheduled study visits, including:

- Visit 1: Includes screening, baseline and fitting of both study lenses
- Visit 2: Dispense of lens pair #1 (If appropriate can be combined with visit 1)
- Visit 3: 1-month follow-up visit of lens pair #1 (30±3 days after dispense)
- Visit 4: Dispense of lens pair #2 (is normally combined with visit 3)
- Visit 5: 1-month follow-up visit for lens pair #2 (30±3 days after dispense) and study exit.

A scheduled follow-up visit may only take place when the participant attends wearing the study lenses for at least four hours. If this is not the case and the participant is not experiencing any problems with the lenses, the appointment will be rescheduled, ideally within the visit window.

Visits that fall outside of the specified visit windows will be designated as protocol deviations and at the end of the study the data collected will be assessed for its suitability to be included in the analysis population.

4.8.1 STUDY VISITS

The summary of visit codes is shown in Table 2.

Table 2: Summary of visit codes

Visit #	Visit code	Visits	25 (2
---------	------------	--------	-------

Visit 1	V1 (V1-R1,& V1-R2 for rescreening if required)	Screening, baseline & fit of both study lens (day 0)
Visit 2	V2	Dispense lens pair #1 (day 0)
Visit 3	V3	1-month follow-up of pair #1 (30±3 days after dispense of pair #1)
Visit 4	V4	Dispense lens pair #2
Visit 5	V5	1-month follow-up of pair #2 (30±3 days after dispense of pair #2)
Exit Visit	any	Study exit

4.8.2 SCREENING

All participants who sign the informed consent letter will be assigned a study ID number. The investigator will determine participant eligibility using the inclusion and exclusion criteria. Ineligible participants will be discontinued from the study. The procedures to be performed are outlined below:

The participant is expected to attend the screening / baseline visit not wearing their habitual contact lens products, instead wearing their spectacles.

The participant will be required to read and sign an Informed Consent Form (Appendix 1) prior to enrollment. When the participant has signed the consent form, the participant will be considered to be enrolled in the study.

Participant demographics and medical history (age, sex, medical conditions, medications, allergies)

Contact lens history (habitual lens information and wearing habits)

The investigator will confirm that the participant meets the eligibility specifications set out in the inclusion criteria and exclusion criteria and is eligible to continue in the study.

Trial fitting of both study lenses will be done:

- The contact lenses will be provided to participants in a manner which does not unmask the participant, as described in Section 4.7.4.
- The lenses will be inserted by the participant.

